5.4 Follow-up visits

Patients will return for follow-up visits at 2, 4, 12, 24, 36, 48, 60, 72, and 96 weeks after randomization. Each visit will have an interval of time surrounding the ideal date for the visit during which the visit may be done and the data included in the trial database. The ideal target date for a visit is the exact anniversary from randomization. Visit windows will be constructed to be contiguous, so that at any point in time, a follow-up visit window is open. The specific procedures to be completed at each of the follow-up visits are described below.

Week 2 and 4 visits

Follow-up medical history including review of medications, adverse events and study drug compliance, and interim alcohol consumption. These two visits may be conducted by telephone interview. Remind patient not to take study medication on the day of the week 12 visit until the visit has been completed.

Week 12 visit

Follow-up medical history including review of medications, adverse events, and interim alcohol

consumption; focused physical examination, including height, weight, and vital signs (blood pressure, heart rate, respiratory rate, and body temperature). Draw blood for laboratory testing (hepatic panel (total bilirubin, direct bilirubin, AST, ALT, alkaline phosphatase, GGT), fasting lipid profile (total cholesterol, triglyceride, LDL, HDL), and fasting glucose and insulin). Draw 10 mL of blood for serum and 10 mL of blood for plasma banking (including measurements for free fatty acids, bile acids, FGF-19 and CK-18) at the NIDDK Biosample Repository. Women of childbearing potential must have a negative pregnancy test to continue on study drug. Dispense study drug and review study drug adherence with patient. Remind patient not to take study medication on the day of the week 24 visit until the visit has been completed.

Week 24 visit

Follow-up medical history including review of medications, adverse events, and interim alcohol consumption; HRQOL questionnaire; cardiovascular risk factors assessment; detailed physical examination, including height, weight, waist and hip measurements, vital signs (blood pressure, heart rate, respiratory rate, and body temperature), examination for sclera icterus and pedal edema and auscultation of the heart and lungs; and general physical findings, including hepatosplenomegaly, peripheral manifestations of liver disease, ascites, wasting or fetor. Draw blood for laboratory testing (complete blood count (Hgb, WBC, platelet count, MCV, hematocrit), metabolic panel (sodium, potassium, chloride, bicarbonate, calcium, phosphate, BUN, creatinine, uric acid, albumin, total protein), hepatic panel (total bilirubin, direct bilirubin, AST, ALT, alkaline phosphatase, GGT), fasting lipid profile (total cholesterol, triglyceride, LDL, HDL), fasting glucose, insulin, and HbA1c). Draw 10 mL of blood for serum and 10 mL of blood for plasma banking (including measurements for free fatty acids, bile acids, FGF-19, and CK-18) at the NIDDK Biosample Repository. Women of childbearing potential must have a negative pregnancy test to continue on study drug. Dispense study drug and review study drug adherence with patient. Remind patient not to take study medication on the day of the week 36 visit until the visit has been completed.

Week 36 visit

Follow-up medical history including review of medications, adverse events, and interim alcohol consumption; focused physical examination, including height, weight, and vital signs (blood pressure, heart rate, respiratory rate, and body temperature). Draw blood for laboratory testing (hepatic panel (total bilirubin, direct bilirubin, AST, ALT, alkaline phosphatase, GGT), fasting lipid profile (total cholesterol, triglyceride, LDL, HDL), and fasting glucose, and insulin. Draw 10 mL of blood for serum and 10 mL of blood for plasma banking (including measurements for free fatty acids, FGF-19, and CK-18) at the NIDDK Biosample Repository. Women of childbearing potential must have a negative pregnancy test to continue on study drug. Dispense study drug and review study drug adherence with patient. Remind patient not to take study medication on the day of the week 48 visit until the visit has been completed.

Week 48 visit

Follow-up medical history including review of medications, adverse events, and interim alcohol consumption; HRQOL questionnaire; cardiovascular risk factors assessment; detailed physical examination, including height, weight, waist and hip measurements, vital signs (blood pressure, heart rate, respiratory rate, and body temperature), examination for sclera icterus and pedal edema and auscultation of the heart and lungs; and general physical findings, including hepatosplenomegaly, peripheral manifestations of liver disease, ascites, wasting or fetor. Draw blood for laboratory testing (complete blood count (Hgb, WBC, platelet count, MCV, hematocrit), metabolic panel (sodium, potassium, chloride, bicarbonate, calcium, phosphate, BUN, creatinine, uric acid, albumin, total protein), hepatic panel (total bilirubin, direct bilirubin, AST, ALT, alkaline phosphatase, GGT), fasting lipid profile (total cholesterol, triglyceride, LDL, HDL), fasting glucose, insulin, and HbA1c. Draw 10 mL of blood for serum and 10 mL of blood for plasma banking (including measurements for free fatty acids, bile acids,

FGF-19, and CK-18) at the NIDDK Biosample Repository. Women of childbearing potential must have a negative pregnancy test to continue on study drug. Dispense study drug and review study drug adherence with patient. Remind patient not to take study medication on the day of the week 60 visit until the visit has been completed.

Week 60 visit

Follow-up medical history including review of medications, adverse events, and interim alcohol consumption; focused physical examination, including height, weight, and vital signs (blood pressure, heart rate, respiratory rate, and body temperature). Draw blood for laboratory testing (hepatic panel (total bilirubin, direct bilirubin, AST, ALT, alkaline phosphatase, GGT), fasting lipid profile (total cholesterol, triglyceride, LDL, HDL), and fasting glucose and insulin. Draw 10 mL of blood for serum and 10 mL of blood for plasma banking (including measurements for free fatty acids, FGF-19, and CK-18) at the NIDDK Biosample Repository. Women of childbearing potential must have a negative pregnancy test to continue on study drug. Dispense study drug and review study drug adherence with patient. Remind patient not to take study medication on the day of the week 72 visit until the visit has been completed.

Week 72 visit

Follow-up medical history including review of medications, adverse events, and interim alcohol consumption; HRQOL questionnaire; cardiovascular risk factors assessment; detailed physical examination, including height, weight, waist and hip measurements, vital signs (blood pressure, heart rate, respiratory rate, and body temperature), examination for sclera icterus and pedal edema and auscultation of the heart and lungs; and general physical findings, including hepatosplenomegaly, peripheral manifestations of liver disease, ascites, wasting or fetor. Draw blood for laboratory testing (complete blood count (Hgb, WBC, platelet count, MCV, hematocrit), metabolic panel (sodium, potassium, chloride, bicarbonate, calcium, phosphate, BUN, creatinine, uric acid, albumin, total protein), hepatic panel (total bilirubin, direct bilirubin, AST, ALT, alkaline phosphatase, GGT), fasting lipid profile (total cholesterol, triglyceride, LDL, HDL), fasting glucose, insulin, HbA1c, prothrombin time and INR. Draw 20 mL of blood for serum and 10 mL of blood for plasma banking (including measurements for free fatty acids, bile acids, FGF-19 and CK-18) at the NIDDK Biosample Repository. Blood for serum and plasma banking may be drawn immediately prior to the liver biopsy, but cannot be obtained in the 72 hour period after a liver biopsy. A pregnancy test (for women of child-bearing potential) should be obtained prior to the liver biopsy and MRI exam. Review study drug adherence with patient. Patient would undergo a repeat liver biopsy and an MRI of the liver for fat fraction while patient is still taking the study drug. In addition, patients without a diagnosis of diabetes will also complete a 2 hour OGTT with measurement of glucose and insulin.

Week 96 visit

Follow-up medical history including review of medications, adverse events, and interim alcohol consumption; HRQOL questionnaire; cardiovascular risk factors assessment; detailed physical examination, including height, weight, waist and hip measurements, vital signs (blood pressure, heart rate, respiratory rate, and body temperature), examination for sclera icterus and pedal edema and auscultation of the heart and lungs; and general physical findings, including hepatosplenomegaly, peripheral manifestations of liver disease, ascites, wasting or fetor. Draw blood for laboratory testing (complete blood count (Hgb, WBC, platelet count, MCV, hematocrit), metabolic panel (sodium, potassium, chloride, bicarbonate, calcium, phosphate, BUN, creatinine, uric acid, albumin, total protein), hepatic panel (total bilirubin, direct bilirubin, AST, ALT, alkaline phosphatase, GGT), fasting lipid profile (total cholesterol, triglyceride, LDL, HDL), fasting glucose, insulin, and HbA1c. Draw 10 mL of blood for serum and 10 mL of blood for plasma banking (including measurements for free fatty acids, bile acids, FGF-19 and CK-18) at the NIDDK Biosample Repository. Closeout form will be obtained at this visit.

Patients electing to participate in the NAFLD Adult Database 2 observational study will be followed at subsequent yearly visits.

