- History of biliary diversion
- Known positivity for Human Immunodeficiency Virus infection
- Active, serious medical disease with likely life expectancy less than 5 years
- Active substance abuse including inhaled or injected drugs, in the year prior to screening
- Pregnancy, planned pregnancy, potential for pregnancy and unwillingness to use effective birth control during the trial, breast feeding
- Participation in an IND trial in the 30 days prior to randomization
- Any other condition which, in the opinion of the investigator, would impede compliance or hinder completion of the study
- Failure to give informed consent

Outcome measures

Primary:

Centrally scored histological improvement in NAFLD from baseline to the end of 72 weeks of treatment, where improvement is defined as:

- (1) No worsening in fibrosis; and
- (2) A decrease in NAFLD Activity Score (NAS) of at least 2 points

65 weeks from 1st patient randomized:

Change in serum ALT from baseline to 24 weeks
Adverse events and other safety measures through interim analysis

Secondary changes in the following from baseline to 72 weeks:

NASH diagnosis (from definite or indeterminate NASH to not-NASH)
Fibrosis score
Hepatocellular ballooning score
Each component score in the NAS
Change in serum aminotransferase and gamma-glutamyl transpeptidase (GGT) levels
Change in MRI-determined hepatic fat
Change in fasting markers of insulin resistance (HOMA, adipo-IR index)
Change in post-glucose parameters of insulin (2-hour glucose and fatty acids)
Change in anthropometric measurements (weight, BMI, waist to hip ratio, waist circumference)
Change in bile acid levels
Change in cytokeratin 18 (CK-18) fragment assay
Change in fibroblast growth factor (FGF-19) levels
Change in markers of hepatic apoptosis, inflammation, and fibrosis
Change in health related quality of life (HR-QoL) scores

Screening and enrollment

Up to 16 weeks screening prior to randomization
72-week treatment period
24-week post-treatment washout period
Length of recruitment: 78 weeks (18 months)
Expected enrollment rate: 35 patients each center (~2 patients per month at each center)

Number of clinical centers: 8

Visit schedule:

Screening period can last no more than 16 weeks (112 days) after registration
Randomization: final pre-treatment interview, dispensing of study drug

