Patients who have not had a liver biopsy within 90 days of randomization or whose previous liver biopsy is not available for review or whose previous liver biopsy is of inadequate quality must have a liver biopsy no more than 90 days prior to randomization to be eligible to participate in the FLINT trial. The biopsy should be done once the patient has been found to be eligible with respect to all other criteria. Biopsy tissue should be of adequate size (1.5 cm or more in length and obtained with at least a 16 G instrument) and of adequate quality for interpretation. The patient must have histologic evidence of definite or probable NASH on the baseline liver biopsy and a NAS of 4 or greater with a score of at least 1 in each component of the NAS (steatosis scored 0-3, lobular inflammation scored 0-3, ballooning scored 0-2).

In the case of a biopsy done previously as standard of care, the NASH CRN study physician should check

if tissue blocks and/or additional slides can be obtained from the original biopsy. If the liver biopsy is completed as part of screening for this trial, the liver tissue will be prepared for light microscopy and stains will include hematoxylin and eosin, Masson's trichrome, and iron stain; additionally, a piece of liver tissue will be snap frozen and stored at -70 degrees C and set aside for banking.

Clinic staff should note that the date of the biopsy establishes a hard window for completion of screening for randomization – randomization must take place within 90 days of the date of biopsy. If the biopsy is more than 90 days old when the patient enters screening or if the patient has medications that need to be washed out in the opinion of the site PI, the biopsy will be too old by the time randomization occurs. This will require a new biopsy. Clinic staff will have to monitor completion of screening procedures and speed things up if the closing date on the 90 day biopsy window is getting close.

Baseline MRI

Patients who agree to have optional MRI studies as part of the FLINT trial and who have provided additional consent will undergo MRI assessment of liver fat at a point between screening and randomization in accordance with the plan as outlined below. The MRI exam must be performed no more than 90 days from the time of biopsy and done prior to randomization.

Screening visit 2

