 - Pregnant or trying to become pregnant
 - Weight or girth exceeds the scanner capabilities
 - Any condition or circumstance that, in the opinion of the site investigator, would interfere with completion of MR examinations

Safety screening

Clinical sites will screen subjects for MRI safety per institutional standards.

Exam scheduling

Subjects will undergo two MRI examinations. The first MRI exam will be performed after screening but prior to treatment randomization as contemporaneously as possible to, and no more than 90 days from the baseline biopsy. The second MRI exam will be performed as contemporaneously as possible to, and no more than 6 weeks before and no more than 12 weeks after the post-treatment biopsy. The goal will be to schedule the second MRI exam at the same or similar time of day as the first MRI exam. Clinical sites will determine the logistics of scheduling the MRI exam.

Pre-MRI exam instructions

Subjects will be instructed, if possible, to fast for 4 or more hours prior to the scheduled MRI exam but will be allowed to take necessary medications and small quantities of water.

Exam performance

Subjects will be positioned supine with a phased-array coil centered over the liver. After localizing sequences, an axial multi-echo-echo 2D FSPGR sequence will be performed through the liver. Imaging parameters will be selected as appropriate for 1.5T or 3T scanners. After completion of the exam, clinical sites will transfer MR images to the Radiology Reading Center (RRC). The RRC will be run through the Department of Radiology at University of California, San Diego.

Exam analysis

Image analysts at the RRC will review and analyze images. The analysts will place regions of interest in each hepatic segment. The fat fraction in each region of interest will be calculated using custom software developed by the RRC and validated in clinical patients and research subjects with liver fat fraction values ranging from <1% to >40%.^{90,91} The fat fraction in each region of interest will be recorded. The average fat fraction across segments will be calculated.

Data transmittal

The average hepatic fat fraction value calculated in each subject on each of the two MRI exams will be transmitted by the RRC to the Data Coordinating Center (DCC).

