5.8 Liver biopsy

Liver biopsies will be performed 72 weeks after enrollment (window: 66-78 weeks) by the NASH CRN principal investigator designee. End-of-treatment liver biopsies will not be performed until the NIDDK program official has given approval to continue the FLINT trial based on safety and efficacy data obtained from the interim vanguard analysis.

Liver biopsies will generally be obtained from the right lobe of the liver using a 16G or larger biopsy

instrument. If the initial biopsy was obtained from the left lobe, then the 72 week biopsy must be obtained from the left lobe. Biopsies should be at least 1.5 cm in length.

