7.1 Hypotheses and outcome measures

Primary Hypothesis

Obeticholic acid at 25 mg orally once daily for 72 weeks is better than placebo in improving liver histologic parameters as measured by the NAFLD activity score in patients with biopsy evidence of nonalcoholic steatohepatitis.

The ***primary outcome measure*** requires the following two conditions:

- No worsening of the fibrosis score
- A decrease in NAS by 2 or more points

Secondary Hypotheses

- Administration of the farnesoid X receptor ligand obeticholic acid for 72 weeks to subjects with biopsy evidence of nonalcoholic steatohepatitis will result in improvement in insulin sensitivity as measured by HOMA-IR and the adipo-IR index.
- Administration of the farnesoid X receptor ligand obeticholic acid for 72 weeks to subjects with biopsy evidence of nonalcoholic steatohepatitis will result in reduction in MRI-determined hepatic fraction.
- Administration of the farnesoid X receptor ligand obeticholic acid for 72 weeks to subjects with biopsy evidence of nonalcoholic steatohepatitis will result in a greater decrease in the proportion of patients with a biopsy diagnosis of definite or probable NASH compared to placebo
- Administration of the farnesoid X receptor ligand obeticholic acid for 72 weeks to subjects with biopsy evidence of nonalcoholic steatohepatitis will result in reduction in serum aminotransferase and gamma-glutamyl transpeptidase.

Secondary outcome measures

- Change in histological diagnosis from NASH or indeterminate for NASH to not-NASH
 - Whereas the primary endpoint is based on changes of specific features of NASH as summed in the NAS, it does not actually evaluate whether NASH resolves with treatment. Thus this essential secondary endpoint of determining whether NASH resolves with treatment will be a major outcome of the trial.
 - It will be anticipated that some subjects judged to have NASH on their locally read entry biopsy will not have NASH on central reading of deeper cuts from the same block.
 - For the purposes of this analysis, subjects with borderline NASH will be included with subjects with definite NASH.
- Mean changes in NAS
- Changes in individual histological characteristics:
 - Mean fibrosis score
 - Change from stage 1b to 1a fibrosis
 - Steatosis
 - Lobular inflammation
 - Portal chronic inflammation
 - Ballooning
 - Other specific features from the histologic scoring system
- Changes in serum aminotransferase levels:
 - Mean change in ALT, AST, and GGT

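### The second-MRI window in 5.7 allows scans up to 12 weeks after the biopsy with no on-drug condition, although 5.4 requires the scan on study drug

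*Protocol*

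**What the plan says.** Two sections of the protocol govern the timing of the end-of-treatment MRI.

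- Section 5.4, week 72 visit: "Patient would undergo a repeat liver biopsy and an MRI of the liver for fat fraction while patient is still taking the study drug".
- Section 5.7, exam scheduling: the second scan is to be done "as contemporaneously as possible to, and no more than 6 weeks before and no more than 12 weeks after the post-treatment biopsy". Nothing there refers to study drug, and the logistics are left to the clinical sites.

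The baseline scan is treated differently. Section 5.7 says "The first MRI exam will be performed after screening but prior to treatment randomization", and section 5.2 repeats the condition: "The MRI exam must be performed no more than 90 days from the time of biopsy and done prior to randomization". Only the second scan lacks a tie to treatment state in its scheduling rule.

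Other relevant provisions:

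- Section 5.8 sets the biopsy at week 72, with a window of weeks 66 to 78.
- Section 3.1 gives 72 weeks of treatment followed by a 24-week washout, which is there to see whether effects last and to check safety.
- Section 5.6 lists week 60 as the last dispensing visit.
- The synopsis lists "Change in MRI-determined hepatic fat" under the line "Secondary changes in the following from baseline to 72 weeks".
- Section 7.1 has a secondary hypothesis that 72 weeks of obeticholic acid "will result in reduction in MRI-determined hepatic fraction".

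**The concern.** A site that books scans from 5.7 can keep within its stated limit and image a patient who stopped treatment weeks earlier. Such a scan shows how much of the effect persists off drug. The outcome and the hypothesis concern the effect at the end of 72 weeks of treatment. If late scans enter the comparison as 72-week values, the analysis mixes two questions. Should liver fat return off drug, late scans in the active arm would shrink the between-group difference.

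**Working it through.** The protocol states no figure of its own for this point, so the check is calendar arithmetic on its windows.

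**Inputs.** Biopsy at week 66, 72 or 78 (5.8). MRI from 6 weeks before to 12 weeks after the biopsy (5.7). Treatment to week 72, then 24 weeks of washout (3.1). Weeks count from randomization, which section 5.3 equates with enrollment.

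**Formulas.** Earliest scan = biopsy week − 6. Latest scan = biopsy week + 12. Weeks off drug at the latest scan = latest scan − last dose. Share of washout = weeks off drug / 24.

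The protocol does not fix the last dose for a late biopsy, so two assumptions are shown:

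- A: the last dose is at the later of week 72 and the biopsy. This favours the protocol, because 5.4 also wants the biopsy on drug.
- B: the last dose is at week 72, as 3.1 states.

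| Biopsy week | MRI allowed by 5.7 | Off drug at latest scan, A | Off drug at latest scan, B |
|---|---|---|---|
| 66 | 60 to 78 | 78 − 72 = 6 weeks (25%) | 78 − 72 = 6 weeks (25%) |
| 72 | 66 to 84 | 84 − 72 = 12 weeks (50%) | 84 − 72 = 12 weeks (50%) |
| 78 | 72 to 90 | 90 − 78 = 12 weeks (50%) | 90 − 72 = 18 weeks (75%) |

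**How much of the 12-week allowance can be used on drug?** Under A, the time between biopsy and last dose is 72 − 66 = 6 weeks for a week-66 biopsy, 72 − 72 = 0 for week 72, and 78 − 78 = 0 for week 78. For a biopsy on or after week 72, none of the post-biopsy allowance is compatible with 5.4.

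**Could dosing simply continue until a late scan?** The protocol makes no provision for it. Drug is handed out every 12 weeks, the last time at week 60, and the week 72 visit reviews adherence without dispensing.

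**Size of the effect.** No calculation is possible. The protocol gives neither the number of scans expected after the last dose nor a rate at which liver fat returns. The nearest statement is in section 2.5, where the ALT improvement on thiazolidinediones was lost once they were stopped. That is another drug and another measure. It makes the concern plausible but supplies no rate.

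**The case against.** The strongest reply is that the sections add up. Section 5.4 sets a treatment-state condition and 5.7 a maximum distance from the biopsy, and a site that follows both scans on drug. The visit schedule in 10.2 also places the MRI at week 72, the outcome is a change to 72 weeks, and 5.7 itself asks for the scan as near the biopsy as can be managed. The document history records that the 2011 version clarified the timing between biopsy and MRI, so the width may be deliberate, to avoid losing optional scans. Week 90 needs two extremes at once.

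Much of this stands. A reader might infer that the protocol endorses off-drug scans, or that scans at weeks 84 to 90 are to be expected. It supports neither: 5.4 rules such scans out, and the late dates are permitted limits with no stated frequency. What remains is that the joint reading makes most or all of the 12-week allowance unusable, and 5.7 does not say so to the sites that schedule from it. A statistical analysis plan, not among the documents at hand, could settle how late scans are analysed, but the scheduling rule belongs to the protocol.

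It is also fair to object to a hard cut-off that discards scans. It would drop a completer scanned 2 weeks after the last dose, keep an early stopper scanned long after theirs, and turn late scans into missing data. The remedy has to avoid that.

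**Conclusion.** The mismatch is real and worth correcting, but its reach is small. Section 5.7 read alone accepts scans that 5.4 excludes: week 84 after an on-target biopsy, and week 90 only in the extreme case. These come up to 12 weeks after the last dose if dosing continues to the later of week 72 and the biopsy, or up to 18 weeks if dosing always ends at week 72.

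Only the secondary MRI fat-fraction outcome is touched, in the patients who take up the optional MRI (5.2, 7.1). A reader might infer that this outcome is biased toward no difference. The documents support only a conditional statement: if liver fat returns off drug and late scans occur, the difference would be diluted by an unknown amount. A reader might also extend the point to the primary outcome. Nothing here shows that, because the 12-week allowance applies to the MRI and the biopsy keeps its own window.

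**What to change.** Amend the second-MRI sentence in 5.7:

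- For patients still on treatment, schedule the scan within 6 weeks before the biopsy, or after it but before the last dose of study drug, as 5.4 already requires.
- For patients who stopped drug early, scan within weeks 66 to 78 and keep them under intention-to-treat. This fits section 5.10, which keeps patients taken off drug for side effects in follow-up.
- Record the last-dose date. If a completer is scanned after the last dose, keep the scan in the main analysis, flag it, and run a sensitivity analysis without the flagged scans.

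The cost is a tighter span for an optional scan. For a week-72 biopsy with the last dose that day, it falls from 84 − 66 = 18 weeks to 72 − 66 = 6 weeks. That span still includes the week 72 visit, where the scan is already scheduled. One date and one sensitivity analysis are added. No extra drug is needed, the washout is unchanged, and no late scan is thrown away.
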